### **Appendix C: Visual Analog Scale**

The Visual Analog Scale (VAS) is a 100-millimeter line with “no pain” on one end and “pain as bad as it can be” at the other end. This scale is a very simple form of assessment. Patients are expected to mark on the line the amount of pain they are experiencing.

## Appendix E: Neck Disability Index

### Neck Disability Index

This questionnaire has been designed to give us information as to how your neck pain has affected your ability to manage in everyday life. Please answer every section and mark in each section only the one box that applies to you. We realize you may consider that two or more statements in any one section relate to you, but please just mark the box that most closely describes your problem.

#### Section 1: Pain Intensity

- = I have no pain at the moment
- = The pain is very mild at the moment
- = The pain is moderate at the moment
- = The pain is fairly severe at the moment
- = The pain is very severe at the moment
- = The pain is the worst imaginable at the moment

#### Section 2: Personal Care (Washing, Dressing, etc.)

- = I can look after myself normally without causing extra pain
- = I can look after myself normally but it causes extra pain
- = It is painful to look after myself and I am slow and careful
- = I need some help but can manage most of my personal care
- = I need help every day in most aspects of self care
- = I do not get dressed, I wash with difficulty and stay in bed

#### Section 3: Lifting

- = I can lift heavy weights without extra pain
- = I can lift heavy weights but it gives extra pain
- = Pain prevents me lifting heavy weights off the floor, but I can manage if they are conveniently placed, for example on a table
- = Pain prevents me from lifting heavy weights but I can manage light to medium weights if they are conveniently positioned
- = I can only lift very light weights
- = I cannot lift or carry anything

**Section 4: Reading**

- = I can read as much as I want to with no pain in my neck
- = I can read as much as I want to with slight pain in my neck
- = I can read as much as I want with moderate pain in my neck
- = I can't read as much as I want because of moderate pain in my neck
- = I can hardly read at all because of severe pain in my neck
- = I cannot read at all

**Section 5: Headaches**

- = I have no headaches at all
- = I have slight headaches, which come infrequently
- = I have moderate headaches, which come infrequently
- = I have moderate headaches, which come frequently
- = I have severe headaches, which come frequently
- = I have headaches almost all the time

**Section 6: Concentration**

- = I can concentrate fully when I want to with no difficulty
- = I can concentrate fully when I want to with slight difficulty
- = I have a fair degree of difficulty in concentrating when I want to
- = I have a lot of difficulty in concentrating when I want to
- = I have a great deal of difficulty in concentrating when I want to
- = I cannot concentrate at all

**Section 7: Work**

- = I can do as much work as I want to
- = I can only do my usual work, but no more
- = I can do most of my usual work, but no more
- = I cannot do my usual work
- = I can hardly do any work at all
- = I can't do any work at all

**Section 8: Driving**

- = I can drive my car without any neck pain
- = I can drive my car as long as I want with slight pain in my neck
- = I can drive my car as long as I want with moderate pain in my neck
- = I can't drive my car as long as I want because of moderate pain in my neck
- = I can hardly drive at all because of severe pain in my neck
- = I can't drive my car at all

**Section 9: Sleeping**

- = I have no trouble sleeping
- = My sleep is slightly disturbed (less than 1 hr sleepless)
- = My sleep is mildly disturbed (1-2 hrs sleepless)
- = My sleep is moderately disturbed (2-3 hrs sleepless)
- = My sleep is greatly disturbed (3-5 hrs sleepless)
- = My sleep is completely disturbed (5-7 hrs sleepless)

**Section 10: Recreation**

- = I am able to engage in all my recreation activities with no neck pain at all
- = I am able to engage in all my recreation activities, with some pain in my neck
- = I am able to engage in most, but not all of my usual recreation activities because of pain in my neck
- = I am able to engage in a few of my usual recreation activities because of pain in my neck
- = I can hardly do any recreation activities because of pain in my neck
- = I can't do any recreation activities at all

**Scoring:**

For each section the total possible score is 5:

If the first statement is marked the section score = 0, if the last statement is marked it = 5.

Score: \_\_\_\_/50      Transform to percentage score  $\times 100 = \%$ points

## Appendix F: SF-12 Health Survey

### SF-12 HEALTH SURVEY (STANDARD)

**INSTRUCTIONS:** This questionnaire asks for your views about your health. This information will help keep track of how you feel and how well you are able to do your usual activities.

Please answer every question by marking one box. If you are unsure about how to answer, please give the best answer you can.

1. In general, would you say your health is:

- |                          |                          |                          |                          |                          |
|--------------------------|--------------------------|--------------------------|--------------------------|--------------------------|
|  |
| Excellent         | Very good         | Good              | Fair              | Poor              |

The following items are about activities you might do during a typical day. Does your health now limit you in these activities? If so, how much?

- |   | Yes,
Limited
A Lot | Yes,
Limited
A Little | No, Not
Limited
At All |
|---|-----------------------------------|--------------------------------------|---------------------------------------|
| 2. Moderate activities , such as moving a table, pushing a vacuum cleaner, bowling or playing golf |           |              |               |
| 3. Climbing several flights of stairs  |           |              |               |

During the past 4 weeks, have you had any of the following problems with your work or other regular daily activities as a result of your physical health?

- |  | Yes               | No                |
|--|--------------------------|--------------------------|
| 4. Accomplished less than you would like                |  |  |
| 5. Were limited in the kind of work or other activities |  |  |

During the past 4 weeks, have you had any of the following problems with your work or other regular daily activities as a result of any emotional problems (such as feeling depressed or anxious)?

- |  | Yes               | No                |
|--|--------------------------|--------------------------|
| 6. Accomplished less than you would like                    |  |  |
| 7. Didn't do work or other activities as carefully as usual |  |  |

8. During the past 4 weeks, how much did pain interfere with your normal work (including both work outside the home and housework)?

- |                          |                          |                          |                          |                          |
|--------------------------|--------------------------|--------------------------|--------------------------|--------------------------|
|  |
| Not at all        | A little bit      | Moderately        | Quite a bit       | Extremely         |

These questions are about how you feel and how things have been with you during the past 4 weeks. For each question, please give the one answer that comes closest to the way you have been feeling. How much of the time during the past 4 weeks –

	All of the Time	Most of the Time	A Good Bit of the Time	Some of the Time	A Little of the Time	None of the Time
9. Have you felt calm and peaceful?						
10. Did you have a lot of energy?						
11. Have you felt downhearted and blue?						
12. During the past 4 weeks , how much of the time has your physical health or emotional problems interfered with your social activities (like visiting with friends, relatives, etc.)?						
	All of the time	Most of the time	A Good Bit of the time	Some of the time	A little of the time	None the time

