H. OMT, BEMER, and placebo will be performed by osteopathic medical students who have completed additional training given by a licensed osteopathic physician to ensure uniform technique. A licensed osteopathic physician will be in the vicinity of the treatment location at all times while treatments are being given.

I. All data collection logs will be de-identified of personal information and only contain the randomized participant ID number linking the participant to the data collected.

J. The identifying information will be maintained by the principal investigator in a locked cabinet, which they alone have access to.

II. Study Procedures and Timeline

A. Study duration

1. The study duration is three weeks. The subjects will be required to have either OMT, BEMER, OMT+BEMER, or Placebo treatments during the course of the study. Each subject in the OMT groups (i.e. OMT and OMT+BEMER) will receive treatment 3 times per week for a period of 3 weeks. Subjects in the BEMER groups (i.e. BEMER and OMT+BEMER) will receive treatment 5 times per week for a period of 3 weeks. Finally, subjects in the Placebo group will receive the combined light touch and BEMER sham treatments at same intervals as the corresponding experimental groups. OMT, BEMER, and placebo treatments will be performed by osteopathic medical students who have completed additional training given by a licensed osteopathic physician, to ensure uniform technique.
2. Recruitment:
  - a) LECOM-Bradenton faculty, staff, osteopathic medical, dental, pharmacy, and master's students will be informed via email of the opportunity to participate in the research study and will be given contact information to confirm eligibility with a study coordinator (Appendix A).
3. Experimental Sessions
  - a) Following written consent (Appendix B), subjects will be given a randomized study ID number. They will be randomized into their treatment group.

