  - b) Each subject in the OMT groups (i.e. OMT and OMT+BEMER) will receive treatment 3 times per week for a period of 3 weeks. As previously mentioned, subjects in the BEMER groups (i.e. BEMER and OMT+BEMER) will receive treatment 5 times per week for a period of 3 weeks. Finally, subjects in the Placebo group will receive the combined light touch and BEMER sham treatments at same intervals as the corresponding experimental groups. OMT, BEMER, and placebo treatments will be performed by osteopathic medical students who have completed additional training given by a licensed osteopathic physician, to ensure uniform technique. All treatments will be performed during the span of three consecutive weeks.
  - c) Subjects will complete brief questionnaires regarding neck pain and quality of life before the beginning of study and will complete the same questionnaires following the completion of the three week treatment (Appendices C, E, F).

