### III. Analysis

#### A. Study Statistics

1. Primary outcome variable
  - a) Questionnaire ratings before and after treatments
    - (1) Neck Disability Index (Appendix E) [28-31]
    - (2) SF-12 Health Survey (Appendix F) [32]
    - (3) Visual Pain Analog (Appendix C) [33]
2. Statistical plan including sample size justification and interim data analysis
  - a) Paired T-tests (N~10 subjects) to investigate the changes in neck pain after each treatment protocol.
  - b) One-Way ANOVA to investigate any statistically significant differences between the means of each of the 4 experimental groups.
3. Early stopping rules

- a) Any adverse effect, as determined by the attending licensed osteopathic physician. No adverse effects are anticipated.
- B. Blinding
  - 1. All outcome analyses will be performed in a blinded fashion. Subject survey and corresponding data will be de-identified and analyzed retrospectively by investigators with no exposure to the treatment sessions. Doing so will eliminate bias associated with investigator self-interest and ensure subject anonymity.

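### Nine of the 12 SF-12 items look back 4 weeks over a three-week treatment, and neither form has a set day, so a prompt post-treatment form also covers 7 to 9 pre-treatment days

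*Combined protocol and SAP*

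**What the plan says.** Section III.A.1 (Study Statistics) lists the SF-12 with the Neck Disability Index (NDI) and the visual analog scale (VAS) as the primary outcome variable, under "Questionnaire ratings before and after treatments".

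The recall periods of the SF-12 are printed in Appendix F:

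- Item 1 asks about health in general and has no look-back.
- Items 2 and 3 ask about the present: "Does your health now limit you in these activities".
- Items 4 to 7 are yes/no items under the stem "During the past 4 weeks, have you had any of the following problems with your work or other regular daily activities". The stem appears once for physical health and once for emotional problems.
- Item 8 reads "During the past 4 weeks, how much did pain interfere with your normal work".
- Items 9 to 11 share the stem "How much of the time during the past 4 weeks".
- Item 12, on social activities, uses the same 4-week period.

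On the length of treatment, section II.A.1 states "The study duration is three weeks", and II.A.3.b states "All treatments will be performed during the span of three consecutive weeks". On the timing of the forms, II.A.3.c says that subjects complete them "before the beginning of study and will complete the same questionnaires following the completion of the three week treatment". Neither form is given a day or a window.

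**The concern.** A before/after comparison is cleanest when the follow-up instrument describes a period in which the treatment was acting. Here most of the SF-12 looks back further than the treatment lasted. A subject who fills in the post form promptly is asked to summarise three weeks of treatment together with a week or so that came before it. If treatment helps, those earlier days pull the post score back towards baseline. Both the change within a group and the difference between groups are then likely to look smaller than they are.

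The affected items include item 8, on pain interfering with work, which is the SF-12 question closest to the aim of the study. The SF-12 is also the plan's only general quality-of-life measure. Because no completion day is set, the mix of days before, during and after treatment can differ from one subject to the next. A null SF-12 result would be hard to interpret.

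**Working it through.** **Items affected.** Counting by stem in Appendix F: items 4–5 (2) + items 6–7 (2) + item 8 (1) + items 9–11 (3) + item 12 (1) = 9 of 12.

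**Inputs.** Recall window: 4 weeks = 28 days (Appendix F). Treatment period: three weeks = 21 days (II.A.1 and II.A.3.b). Day 1 is the first session, so the treatment period is days 1 to 21. Completion day of the post form: not stated, written here as *d*. Day 19 is an assumption. It is the Friday of week 3 if the first session is on a Monday and sessions are on weekdays.

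**Formulas.** The window of a form completed on day *d* runs from day *d* − 27 to day *d*. For completion days 19 to 28:

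- days before the first session = max(0, 28 − *d*)
- days after day 21 = max(0, *d* − 21)

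| Post form completed | Window | Before first session | After day 21 |
|---|---|---|---|
| Day 19 (assumed last weekday session) | −8 to 19 | 28 − 19 = 9 (9/28 = 32%) | 0 |
| Day 21 | −6 to 21 | 28 − 21 = 7 (7/28 = 25%) | 0 |
| Day 24 | −3 to 24 | 28 − 24 = 4 (4/28 = 14%) | 24 − 21 = 3 |
| Day 28 | 1 to 28 | 0 | 28 − 21 = 7 |

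The pre-treatment count falls by one for each day of delay and reaches zero at day 28. By then the window holds 7 days after the treatment period, and more if the form comes later.

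**What this means for the yes/no items.** Items 4 to 7 ask whether any such problem occurred. Take a subject who had the problem on day 0, the day before the first session, and never again. Answered literally, the form still calls for Yes on day 21, because that window starts on day −6. No becomes a correct answer only from day 28, when the window starts on day 1. This illustrates the mechanism. It does not claim that respondents answer so literally.

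**Instruments not affected.** The VAS in Appendix C asks for the pain being experienced, and section 1 of the NDI in Appendix E asks about pain at that moment. Neither has a look-back.

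**Effect of a one-week recall.** The window becomes day *d* − 6 to day *d*: days 13–19 for a form on day 19, and days 15–21 for a form on day 21. Both lie wholly inside the treatment period.

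No effect-size or power figure follows from this. The documents give no SF-12 scoring rule and do not show how respondents weight the days they recall.

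**The case against.** The case on the other side has five parts.

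1. **Days after treatment need not dilute anything.** The outcome is defined as ratings before and after treatment, and is not confined to days 1 to 21. This stands. Since 28 − 21 = 7, a reader might infer that at least a quarter of the recall window is harmful on any completion day. The 7-day minimum outside treatment is correct arithmetic, but it adds together two kinds of day, and only the pre-treatment days clearly dilute. Their number can be zero.

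2. **The form is a standard published instrument.** Appendix F labels it as the standard version, and changing its recall period has a price. This also stands. The documents contain no one-week version, so its existence and scoring must be confirmed first. The standard label does not, however, make a 4-week window fit a three-week treatment.

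3. **The schedule implies completion near day 21.** That is a fair reading of a three-week study. It supports the concern, because prompt completion is when the pre-treatment days are most numerous. Some pages, including the consent form, are not in the public copy and could hold timing detail. The schedule text itself sets no day.

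4. **Respondents may lean on recent days.** Possibly. For that reason the claim is limited to a tendency of unknown size.

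5. **The study is about neck pain, and the paired t-tests address neck pain.** True, and it limits the consequence. The SF-12 is still listed as a primary outcome questionnaire.

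**Conclusion.** The point holds for the SF-12 only, as a matter of sensitivity and interpretation. If the post form is completed between day 19 and day 21, 9 down to 7 of the 28 recall days behind nine of the 12 items precede treatment. This tends to shrink SF-12 change and SF-12 differences between groups. The size cannot be derived from the documents. The counts assume a 21-day treatment period beginning with the first session. The day-19 figure also assumes a Monday start with weekday sessions.

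Two stronger readings should be avoided. A reader might infer that the problem is identical in all four arms and so cannot affect the comparison. The documents show this only for the wording, which does not by itself favour an arm. With no form day set, and with OMT given 3 times and BEMER 5 times a week, the mix of days can vary between subjects, and equality across arms is not assured. Nor do the documents show that any arm is in fact favoured. A reader might also infer that the primary outcome as a whole is compromised. It is not: the VAS and NDI section 1 ask about current pain.

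This is an inexpensive improvement to make before enrolment. It is not a flaw that undermines the trial.

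**What to change.** **Set the days.** In II.A.3.c, name the completion day of each form, the same for all four arms: baseline immediately before the first session, and the post form between the last session and day 21. Record both dates for every subject. This costs one sentence and two recorded dates, with no extra visit, and it removes the variation between subjects whichever form is used.

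**Match the recall.** Use a one-week recall for items 4 to 12 at both time points, provided that a scorable one-week version is confirmed first. The cost is a wording change to nine items, the check on scoring, and less comparability with studies that use the 4-week form.

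**If that cannot be confirmed,** keep the 4-week form on the same fixed days. State in the report that the post SF-12 covers a window including 7 to 9 pre-treatment days, according to the day chosen, and do not read a null SF-12 result as absence of effect. Beyond the recorded dates, this costs a short reporting statement.
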